The secondary objective is to compare the effectiveness of Cognitive Processing Therapy and Accelerated Resolution Therapy in reducing depression symptom severity.

C. Tertiary Objective

The tertiary objective is to examine whether treatment effectiveness is reduced when patient preference for treatment is incongruent with their random assignment.

D. Exploratory Analyses

Exploratory analyses will be performed to examine whether demographic (e.g., sex, age, Veteran/Non-Veteran status) and other clinically-relevant variables (e.g., sleep quality, anger, pain, health care utilization) predict differential response and/or drop-out across treatment condition.

III. Study Design

This study will examine the effectiveness of Cognitive Processing Therapy (CPT) as compared to Accelerated Resolution Therapy (ART) and a Wait list (WL) control using a Randomized, Cross-Over Design with blinded assessment. 280 participants will be randomly assigned to receive ART, CPT or WL condition. Upon completion of the WL condition after 7 weeks, participants will be re-randomized to ART or CPT.

The primary outcome is improvement in PTSD symptom severity as measured by change on the Clinician-Administered PTSD Scale for DSM-IV or DSM-5 (CAPS-IV/ CAPS-5) after treatment. This primary outcome measure will be administered by post-doctoral fellows in psychology who will remain blinded to treatment condition. The

CAPS-IV and CAPS-5 will be administered at pre- and post-treatment, and 3-month and 1-year follow-up visits.

A. Study Population

Participants will be 280 male and female Veterans and civilians who meet criteria for PTSD, or subthreshold PTSD, due to any Criterion A traumatic event. Subthreshold PTSD occurs when a patient has a Criterion A traumatic event, and endorses symptoms in each of the PTSD Diagnostic Criteria (B-E), but falls below the number and/or severity of total Criterion requirements to meet criteria for a PTSD diagnosis. Inclusion and exclusion criteria and recruitment are described in Section IV.

1. Rationale for Inclusion of Non-Veteran participants

Civilians will be included in this study as they have different Criterion A traumatic events (e.g., non-combat). It is imperative to the primary study objective to assess the comparative effectiveness of CPT and ART across a variety of trauma(s).

B. Study Treatment Conditions

1. Treatment Conditions

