* Prior to the phone screen, participants will be asked to identify how they learned about the study and which site (UC or VA) they were referred from. Veteran participants may be seen at the Cincinnati VAMC or the UC Health Stress Center depending on their associated site. All civilian participants will be seen at the UC Health Stress Center.

D. Outcome Measures

The primary outcome is improvement in PTSD symptom severity as measured by clinically significant change on the Clinician-Administered PTSD Scale for DSM-IV or DSM-5 (CAPS-IV/CAPS-5).

A complete description of all of the outcome measures is in Appendix B.

E. Sample Size and Planned Statistical Analyses

1. Planned Statistical Analyses

The primary objective is to compare the effectiveness of CPT and ART in reducing the primary outcome -- PTSD symptom severity -- for Veteran and civilian patients with PTSD. We predict that CPT will be significantly superior to WL (and potentially superior to ART) in reducing PTSD symptoms post-treatment. To test this hypothesis we will use a 3 (Group: CPT, ART, WL) x 4 (Time: Baseline, Post-treatment) mixed-model ANCOVA covarying for baseline PTSD ratings. A significant omnibus interaction, and lower-order interactions, in the hypothesized direction will confirm this hypothesis.

The secondary objective is to compare the effectiveness of CPT and ART in reducing depression symptom severity. We predict that CPT will be superior to WL (and potentially ART) in reducing depression symptoms post-treatment. We will test this hypothesis with a mixed-model ANCOVA following the same analysis plan as for the primary objective.

The tertiary objective is to examine whether treatment effectiveness is reduced when patient preference for treatment is incongruent with their random assignment as we predict. To test this hypothesis, we will first categorize participants to a dichotomized preference group based on self-report. We will then perform a 2 (Group: Preferred Therapy, Non-preferred Therapy) x 4 (Time: Baseline, Post-Treatment, 3 Month, 1 Year) mixed-model ANCOVA covarying for baseline PTSD for both the primary (PTSD) and secondary (depression) outcome variables. A significant omnibus interaction, and lower-order interactions, in the hypothesized direction will confirm this hypothesis. Additionally, the primary and secondary analyses will be rerun covarying for preference to examine this variable's differential influence on CPT and ART outcomes.

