to identify PTSD symptom reductions over pre-and post-treatment in the WL condition considering the medium ES.

ES was small for active treatment difference between CPT and PCT symptoms post-treatment ($d = 0.16$). No data directly comparing CPT and ART are available in the extant literature. To detect a similarly small difference ($d_s < 0.2$) in PTSD severity means post-treatment with $\alpha = 0.05$, power = 0.80, two-tailed in the proposed study would require at least a total $N = 706$ ($n = 353$ for each active treatment). Therefore, the proposed $N = 240$ would be insufficient to identify statistically significant differences between CPT and ACT post-treatment if we assume a similarly small effect size. The extant literature does not provide ES estimates between CPT vs. WL and ART vs. WL, but these ESs would be expected to be considerably larger than the CPT vs. PCT estimate.

In the absence of prior WL data with which to estimate ES, and considering that we intend to test interaction effects primarily, we estimate the necessary sample size to detect statistically significant Time x Treatment interactions across the entire power and ES range. Results indicate that for the primary analysis we will have sufficient power to detect even small effects with a total sample size = 246 ($n = 123$ per active treatment condition). For the secondary analysis we will have sufficient power to detect even small effects with a total sample size = 138 ($n = 69$ per active treatment condition).

It should be noted that the above calculations are based on simple contrasts between means and hypothetical power functions for the interaction term in repeated measures ANOVA, none of which include covariates. **These estimates are conservative in that inclusion of covariates, as expected in the final analysis, generally increases power and we intend to over-sample minimally to accommodate participant attrition, further assuring adequate power. *The total sample, then, will be N = 240, split equally between the two active treatments.*** This estimate, based primarily on repeated measure ANOVA, is very conservative as it provides a sufficient sample size to detect even small interaction effects. If needed, we propose oversampling by up to 40 participants to account for drop-outs from assessment or to bolster marginal effects.

F. Random Assignment:

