[name], our statistician, has created a randomization table for all participants using a randomized, cross-over design. For participants who are randomized to the Wait List condition, following the completion of this seven week condition, they will be randomized into one of the two active treatment conditions, CPT or ART, using the randomization table (see Appendix C).

IV. Participant Characteristics and Recruitment

A. Inclusion Criteria

Participants will include 280 males and females ages 18 and older who meet criteria for PTSD (or subthreshold PTSD). Individuals will be included regardless of gender, ethnicity, military/civilian status, or type of trauma(s).

Participants must also agree to participate in either treatment, agree to allow IRB-approved study staff to access their medical record to review the extent to which they use UC or VA services before or during the study, have access to a telephone or agree to come into the Cincinnati VAMC, Trauma Recovery Center for the initial set of questions to determine whether they are eligible to participate, and agree to have their assessment and treatment sessions digitally audio recorded.

B. Exclusion Criteria

Participants who 1) meet criteria for unmedicated bipolar, mania, or unmedicated psychotic disorders; 2) meet criteria for a substance use disorder requiring detoxification treatment; 3) have active suicidal or homicidal intent with (a) plan(s) and (a) means; 4) have a medical condition that will interfere with twice weekly therapy sessions will be excluded from the research study; 5) show severe problems with memory or other problems with thinking and reasoning (defined as 1 SD below age-graded norms on the Montreal Cognitive Assessment [MoCA], Nasreddine et al. 2005).

Individuals with a psychotropic medication change within the last 30 days will be asked to stay consistent with their current dose for a minimum of 30 days before admission to the study.

C. Concurrent Treatment

Participants will be asked to refrain from any concurrent psychotherapy that focuses on treating the symptoms of PTSD or related mental health disorders. Exceptions will be made for those active in substance use treatment programs, including 12 step programs and relapse prevention.

D. Recruitment

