Appendix C. Randomization Tables.

1. University of Cincinnati, UC Health Stress Center Site

CPT/ART/WL Randomization Schedule

University of Cincinnati Site

Initial Randomization 1:1:1

block identifier	block size	sequence within block	treatment	provider	code	Participant ID (02-####)
5	48	1	WL		VJ8	
5	48	2	CPT	[name]	QD7	
5	48	3	CPT	[name]	XY8	
5	48	4	CPT	[name]	VN2	
5	48	5	CPT	[name]	AA2	
5	48	6	CPT	[name]	HH2	
5	48	7	ART	[name]	BR1	
5	48	8	ART	[name]	JC1	
5	48	9	ART	[name]	NB1	
5	48	10	ART	[name]	QT5	
5	48	11	WL		RG0	
5	48	12	CPT	[name]	MO9	
5	48	13	WL		AM0	
5	48	14	CPT	[name]	KX8	
5	48	15	WL		CC0	
5	48	16	ART	[name]	CU6	
5	48	17	ART	[name]	XX9	
5	48	18	CPT	[name]	PW2	
5	48	19	CPT	[name]	EK9	
5	48	20	WL		KQ3	
5	48	21	WL		PH6	
5	48	22	ART	[name]	EM1	
5	48	23	WL		DV2	
5	48	24	WL		EP0	
5	48	25	WL		SN1	
5	48	26	CPT	[name]	LY3	
5	48	27	CPT	[name]	GA9	
5	48	28	CPT	[name]	FN5	
5	48	29	WL		DP9	
5	48	30	CPT	[name]	GD7	
5	48	31	ART	[name]	EN6	
5	48	32	WL		ZF6	
5	48	33	ART	[name]	GF7	

5	48	34	WL		RF9
5	48	35	ART	[name]	HW4
5	48	36	ART	[name]	KU9
5	48	37	WL		NK4
5	48	38	CPT	[name]	RD5
5	48	39	WL		JM6
5	48	40	WL		EM0
5	48	41	ART	[name]	XZ3
5	48	42	CPT	[name]	YN8
5	48	43	ART	[name]	OX8
5	48	44	CPT	[name]	WU4
5	48	45	ART	[name]	EE5
5	48	46	WL		KG0
5	48	47	ART	[name]	NN5
5	48	48	ART	[name]	RJ2

Wait-List Randomization 1:1

block identifier	block size	sequence within block	treatment	provider	code	Participant ID (02-####)
6	16	1	CPT	[name]	VJ8-2	
6	16	2	ART	[name]	RG0-2	
6	16	3	CPT	[name]	AM0-2	
6	16	4	CPT	[name]	CC0-2	
6	16	5	CPT	[name]	KQ3-2	
6	16	6	CPT	[name]	PH6-2	
6	16	7	ART	[name]	DV2-2	
6	16	8	CPT	[name]	EP0-2	
6	16	9	ART	[name]	SN1-2	
6	16	10	ART	[name]	DP9-2	
6	16	11	ART	[name]	ZF6-2	
6	16	12	CPT	[name]	RF9-2	
6	16	13	ART	[name]	NK4-2	
6	16	14	CPT	[name]	JM6-2	
6	16	15	ART	[name]	EM0-2	
6	16	16	ART	[name]	KG0-2	

1. Cincinnati VA Medical Center, Trauma Recovery Center Site

CPT/ART/WL Randomization
Schedule
Cincinnati VAMC Site

Initial Randomization 1:1:1

block size	sequence within block	treatment	provider	code	Participant ID (01- ####)
192	1	WL		RL7	
192	2	CPT	[name]	QL9	
192	3	ART	[name]	YU4	
192	4	WL		YJ1	
192	5	WL		OS5	
192	6	CPT	[name]	UB6	
192	7	CPT	[name]	ZR3	
192	8	CPT	[name]	SC9	
192	9	ART	[name]	AR3	
192	10	CPT	[name]	CP5	
192	11	ART	[name]	CH6	
192	12	ART	[name]	KY7	
192	13	CPT	[name]	WC7	
192	14	WL		JE6	
192	15	ART	[name]	AL2	
192	16	CPT	[name]	LK7	
192	17	ART	[name]	SS5	
192	18	CPT	[name] [name]	YR1	

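### Section III.E.2 lets up to 40 participants be added because an effect looks marginal, with no rule or adjusted level, and the document gives both 240 and 280 as the target

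*Combined protocol and SAP*

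**What the plan says.** Section III.E.2 (Sample Size Estimates) concludes: "The total sample, then, will be N = 240, split equally between the two active treatments". It closes with a conditional addition: "If needed, we propose oversampling by up to 40 participants to account for drop-outs from assessment or to bolster marginal effects". Earlier, the same section states that "for the primary analysis we will have sufficient power to detect even small effects with a total sample size = 246".

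Three other places give a different number and attach no condition to it:

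- Section III (Study Design): "280 participants will be randomly assigned to receive ART, CPT or WL condition".
- Section III.A (Study Population): "Participants will be 280 male and female Veterans and civilians who meet criteria for PTSD".
- Section IV.A (Inclusion Criteria): "Participants will include 280 males and females ages 18 and older who meet criteria for PTSD".

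Appendix C, under "Initial Randomization 1:1:1", lists 48 places for the UC site and 192 for the VA site.

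The success criterion in III.E.1 is: "A significant omnibus interaction, and lower-order interactions, in the hypothesized direction will confirm this hypothesis". It names no significance level. Alpha of 0.05, two-tailed, appears only in the power calculations of III.E.2. No section describes an interim look, and section VIII (Data and Safety Monitoring) deals with confidentiality, data storage and record access.

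**The concern.** The extension sentence gives two reasons joined by *or*. The first, loss of assessments, can be judged from a pooled count without sight of results by arm. The second depends on how strong the observed effect is. A trial that enrols more people because its result is nearly significant, and then tests again at the same level, has had two chances to reject. Its false-positive rate is then above the nominal one.

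The document does not say that this will be done, but nothing in it rules it out. No passage fixes when the effect would be examined, what counts as marginal, who decides, or what level the final test uses.

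The two targets make this worse. If 280 was adopted in advance, the conditional sentence is a leftover and the level is safe. If 240 is the plan, the other 40 are discretionary. A final N between 240 and 280 could then be planned enrolment, replacement of missing data, or a response to a marginal p-value, and the document gives no means of telling which.

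**Working it through.** **Inputs from the document.** Base N = 240 and up to 40 more (III.E.2); 280 in III, III.A and IV.A; alpha 0.05 two-sided (III.E.2); allocation 1:1:1 (Appendix C).

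**Assumptions, because the plan states no rule.** When the effect is looked at, which p-values count as marginal, and whether success may be claimed at the look.

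**1. The plan's own figure.** For a groups-by-times interaction, noncentrality is λ = f²·N·m/(1−ρ), with df1 = (k−1)(m−1) and df2 = (N−k)(m−1). Take k = 3 groups and m = 2 times, and assume f = 0.10 and ρ = 0.5 (neither is stated). At N = 246, λ = 0.01 × 246 × 2/0.5 = 9.84 and power is 80.4%, so 246 is reproduced. On the same basis power is 79.3% at 240 and 85.5% at 280.

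**2. Number of places.** UC 48 (16 per arm) + VA 192 (64 per arm) = 240. The wait-list tables (16 and 64 rows) re-randomize the same wait-list participants under codes ending in -2 and add nobody. The 40 extra participants have no places on the lists.

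**3. Assumption A: test at 240, extend if marginal, retest at 280 at 0.05.** The two z-statistics have correlation √(240/280) = 0.926. With c = 1.96 and c_L the z-value at the upper p-limit for extending,

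type I error = 0.05 + 2·[P(c_L < Z₁ < c, Z₂ > c) + P(c_L < Z₁ < c, Z₂ < −c)].

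| Extended when p at 240 is | 1-df test | 2-df omnibus (simulated) |
|---|---|---|
| 0.05–0.10 | 0.061 | 0.061 |
| 0.05–0.20 | 0.066 | 0.067 |
| any value ≥ 0.05 | 0.068 | 0.068 |

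In the first row the excess is 0.0608 − 0.05 = 0.0108. A null result falls in that window with probability 0.05, so 0.0108/0.05, about 22%, of such results become significant after the extension. Retesting after every 10 added participants gives 0.078.

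**4. Assumption B: one earlier look, no early claim, a single final test at 240 or 280.** By simulation:

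| Look at | Extend for p 0.05–0.10 | p 0.05–0.20 | any p ≥ 0.05 |
|---|---|---|---|
| 120 | 0.049 | 0.049 | 0.052 |
| 160 | 0.049 | 0.049 | 0.053 |
| 200 | 0.049 | 0.052 | 0.056 |

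**5. Which claim is exposed, under A** (three-arm simulation, 80 rising to 93.3 per arm):

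- Significant omnibus plus CPT better than WL, under the global null: 0.012 with fixed N, 0.015–0.017 with extension.
- False CPT–ART difference when both therapies beat WL (assumed d = 0.8): 0.050 with fixed N, 0.061–0.068 with extension.
- Bias in the estimated effect: −0.001 to +0.008 SD, which is negligible.

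**6. A level that restores 0.05.** Setting the overall two-look error to 0.05 gives c = 2.091, or 0.0365 two-sided at each look. For an effect with 80% power at a fixed 280, the z-mean is 2.80 at 280 and 2.80 × 0.926 = 2.59 at 240. Power is then 73.7% at a fixed 240 and 78.5% with two looks at 0.0365.

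**The case against.** The strongest reply is that no look at 240 is described. Three sections state 280 without condition, and 280 = 240 + 40. The figures could therefore be a planned sample and a ceiling, or 280 could have been fixed from the start, in which case the level is exactly 0.05. The disputed phrase also closes a paragraph about prospective power and might mean only extra power for borderline effect sizes.

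These readings are possible, but the text does not establish them. The opening condition makes the addition contingent, and no section calls 280 a ceiling. Had 280 been fixed in advance, the conditional sentence would be redundant and the lists would need 280 places.

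Some of the reply stands on size. Outcomes arrive after 5 to 15 sessions and, for some, a 7-week wait. A look made while recruitment continues is therefore closer to Assumption B, where several values do not exceed 0.05. The III.E.1 criterion, read as omnibus plus CPT better than WL, stays well under 0.05 under the global null. The main exposure is the CPT–ART contrast. III.E.1 predicts a CPT advantage there only as a possibility, but it is the primary objective in section II.A.

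That 240 is below 246 matters little: power falls by about one point on the reproduced basis, before any gain from covariates, and type I error is unaffected. A reported count of missing assessments would also explain part of any excess over 240, though not why enrolment was extended.

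**Conclusion.** The concern holds. As written, the plan permits enrolment to depend on the observed effect under an unstated rule, so 0.05 is not guaranteed for the final test. The inflation is modest: at most about 1.8 percentage points for a single unadjusted retest at 280 (0.0676 − 0.05), more with repeated looks, and between slightly below zero and 0.6 points for one earlier look without an early claim. All of these rest on assumed rules. The drop-out reason causes no inflation if it is applied without sight of outcomes by arm.

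The conflict between 240 and 280 needs no assumption. It is in the text, and the Appendix C lists match only the lower figure. This should be fixed. The larger harm is to interpretation: the reason for a final N above 240 could not be established convincingly once results are known.

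**What to change.** Delete the second reason from the extension sentence in III.E.2, then choose one of two options:

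1. Fix N at 280 in advance.
2. Keep 240 and allow enrolment above it, capped at 280, only on a pooled, arm-blind count of missing post-treatment CAPS assessments. A ceiling of 280 leaves 240 assessed at up to 40/280 = 14.3% attrition.

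State the chosen target in III, III.A, III.E.2 and IV.A, and extend the Appendix C lists to cover it. If the sponsor does want to test at 240 and again at 280, both looks should be prespecified, with 0.0365 two-sided at each.

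The cost is one sentence, one consistent number and a list extension. The sponsor gives up only the option to add participants because a result was marginal. Fixing 280 loses no power but commits to 40 more participants. For an effect with 80% power at 280, stopping at 240 gives 74% and the two-look design 78.5%. These power figures depend on that reference effect and ignore attrition.

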Drop Outs: Participants in any of the three conditions (CPT, ART, or WL) who drop out of treatment will be asked to remain in the study for participation in the assessment portion of the study only. Treatment discontinuation will be based on a discussion between the participant, the study therapist, and the research team to determine the best clinical care plan for ongoing treatment. Participants will be discontinued from treatment if they show substantial worsening of PTSD, other symptoms, or functioning requiring lengthy hospitalization if the worsening is due to treatment. If participants decide to discontinue treatment early, they will be asked by their clinician for a reason and if they consent to be contacted for post-treatment assessments. If they agree to be contacted, study staff will contact the participant to schedule their post-treatment assessment immediately following their last treatment session. Participants will also be contacted to participate in the 3 and 12 month follow up assessments. Participants will be reminded of the voluntary nature of this study and their option to withdraw participation at any time.

C. Study Sites

The study will be conducted at the Cincinnati VA Medical Center, Trauma Recovery Center, in Fort Thomas, Kentucky, and at the UC Health Stress Center located in Cincinnati, Ohio.

Table 1.0 Participant Flow Through the Randomized Clinical Trial		
Study Phase (timeline)	Site	Event
Enrollment (2-3 weeks)	VA only	Telephone Screening Phase: Inclusion and Exclusion Criteria assessed & Site Determination for participant*
	VA or UC	Informed Consent, Pre-Treatment Assessment, & Randomization Assigned by sealed envelope opened by participant after site visit
	VA or UC	Phone scheduling of initial session with therapist
Waitlist (if assigned)	VA or UC	Waitlist Condition participants will wait 7 weeks, will receive weekly Phone Check-In calls by study staff (see Appendix A), then will be randomized to CPT or ART
Treatment (5-15 weekly or biweekly sessions)	VA or UC	Treatment begins (session 1)
	VA or UC	Mid-Treatment Assessment (session 2 – 7)
	VA or UC	Treatment Ends (session 5 – 15)
Post-Treatment (1 year)	VA or UC	Post-treatment Assessment
	VA or UC	3-month follow-up Assessment
	VA or UC	1-year follow-up Assessment

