The participant must sign the ICF and the HIPAA Authorization (Cincinnati VAMC site only) before any study procedures are performed. A copy of the signed ICF will be given to the participant. The original signed forms will be filed in the Participant Consent Form Master File, which will be retained at each individual study site. For participant's at the UC Health Stress Center site, a copy of the signed ICF will be scanned into their medical records.

V. Assessments

A. Assessors: Clinical psychology post-doctoral fellows will perform all pre-, post-, and follow-up assessment interviews, and will be trained and supervised by licensed clinical psychologists. The assessors will remain blind to treatment condition throughout the study. Assessors will administer the: Clinician Administered PTSD Scale for DSM-IV and DSM-5 (CAPS-IV/CAPS-5), the Structured Clinical Interview for DSM-5 (SCID-5), the Montreal Cognitive Assessment (MOCA), and the Creative Imagination Scale.

Participants in the two active treatment conditions will complete a self-report assessment battery at pre-treatment, post-treatment, 3 month, and 1-year follow-up.

B. Self-Report Assessments: The self-report assessment forms will be completed by either paper-and-pencil questionnaires or the survey feature in RedCap. For assessments completed in RedCap survey, participants will complete the RedCap survey on a secure laptop computer or tablet at their designated location (connected to VA patient wifi at the Cincinnati VA or UC Health patient wifi at the UC Health Stress Center). Once a self-report survey has been completed by a participant, the RedCap system will not allow a participant access to change their responses. Participants will not have access to any data within RedCap, and will only be able to view their self-

report assessment forms in RedCap Survey mode. Table 2.0 indicates which self-report assessments can be completed by RedCap Survey and which assessments will be conducted by Assessor interview.

All potential participants will complete a pre-treatment assessment. Following their 7 week wait list period, participants in the WL condition undergo their first post-assessment. Their first post-assessment will be entered as their pre-treatment data when they are randomized to the active treatment condition. All participants will be reassessed in-person or by phone following treatment completion (post-treatment) and for their 3-month and 1 year follow-up.

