192	138	ART	[name]	BI4
192	139	CPT	[name]	KU2
192	140	WL		JE8
192	141	ART	[name]	CC9
192	142	WL		SM9
192	143	CPT	[name]	RX7
192	144	WL		WL0
192	145	WL		BB2
192	146	WL		VE0
192	147	ART	[name]	LO2
192	148	WL		IK7
192	149	CPT	[name]	PN3
			[name]	
192	150	ART	[name]	LD4
192	151	ART	[name]	OA5
192	152	WL		PN4
192	153	CPT	[name]	KY5
192	154	WL		KW6
192	155	WL		WO2
192	156	WL		IP0
192	157	ART	[name]	CJ0
192	158	CPT	[name]	BV2
192	159	CPT	[name]	GH7
192	160	WL		PW4

192	161	WL		SK5
192	162	ART	[name]	RT4
192	163	ART	[name]	BT7
			[name]	
192	164	CPT	[name]	RQ3
192	165	WL		FX7
192	166	WL		JQ3
192	167	CPT	[name]	QU5
192	168	CPT	[name]	DU1
192	169	ART	[name]	LL1
192	170	WL		HT1
192	171	CPT	[name]	DM6
192	172	CPT	[name]	VL1
192	173	ART	[name]	GF4
192	174	ART	[name]	XG0
192	175	CPT	[name]	BV8
192	176	WL		VE1
			[name]	
192	177	ART	[name]	PD2
192	178	ART	[name]	GH1
192	179	CPT	[name]	NY2
192	180	WL		NR3
192	181	ART	[name]	BW2
192	182	ART	[name]	XW9
192	183	WL		DS8
192	184	ART	[name]	BY1
192	185	ART	[name]	ZC4
192	186	CPT	[name]	KE6
			[name]	
192	187	CPT	[name]	VS9
192	188	ART	[name]	J18
192	189	ART	[name]	YY5
			[name]	
192	190	ART	[name]	EB5
192	191	CPT	[name]	FM0
192	192	ART	[name]	RG5

Wait-List Randomization 1:1

block identifier	block size	sequence within block	treatment	provider	code	Participant ID (01-####)
4	64	1	ART	[name]	RL7-2	
4	64	2	CPT	[name]	YJ1-2	
4	64	3	ART	[name]	OS5-2	
4	64	4	ART	[name]	JE6-2	
4	64	5	ART	[name]	YH1-2	

4	64	6	CPT	[name]	RW8-2
4	64	7	CPT	[name]	KK2-2
4	64	8	CPT	[name]	GA9-2
4	64	9	CPT	[name]	ZE5-2
4	64	10	CPT	[name]	GA1-2
				[name]	
4	64	11	CPT	[name]	EY5-2
4	64	12	ART	[name]	YU5-2
4	64	13	CPT	[name]	SK9-2
4	64	14	ART	[name]	ML1-2
				[name]	
4	64	15	ART	[name]	LL9-2
4	64	16	CPT	[name]	SX5-2
4	64	17	ART	[name]	NG7-2
4	64	18	CPT	[name]	NN5-2
4	64	19	CPT	[name]	AL4-2
4	64	20	CPT	[name]	QS8-2
4	64	21	ART	[name]	KU7-2
4	64	22	CPT	[name]	BR0-2
4	64	23	CPT	[name]	OS7-2
4	64	24	ART	[name]	WY7-2
4	64	25	ART	[name]	RI3-2
				[name]	
4	64	26	CPT	[name]	KM5-2
					MW9-
4	64	27	CPT	[name]	2
4	64	28	CPT	[name]	BJ8-2
4	64	29	ART	[name]	HA2-2
4	64	30	ART	[name]	BY7-2
4	64	31	ART	[name]	CD2-2
				[name]	
4	64	32	ART	[name]	QI8-2
4	64	33	ART	[name]	CN8-2
4	64	34	CPT	[name]	CC5-2
4	64	35	CPT	[name]	RT3-2
4	64	36	ART	[name]	DQ4-2
4	64	37	ART	[name]	OP1-2
4	64	38	CPT	[name]	VS6-2
4	64	39	CPT	[name]	IF9-2
4	64	40	CPT	[name]	HO4-2
4	64	41	ART	[name]	JA7-2
				[name]	
4	64	42	CPT	[name]	ZG0-2
4	64	43	CPT	[name]	WL8-2

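### The ordered allocation list is printed in the protocol with no stated access limit, so concealment is not assured, least of all for the wait-list re-randomisation

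*Combined protocol and SAP*

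**What the plan says.** Section III.F states that "our statistician, has created a randomization table for all participants using a randomized, cross-over design". It adds that participants who finish the wait are allocated to CPT or ART "using the randomization table (see Appendix C"). Appendix C is named in the protocol's list of contents and is printed in full.

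For each site the appendix has a table headed "Initial Randomization 1:1:1" and another headed "Wait-List Randomization 1:1". Each row has a running number ("sequence within block"), the treatment, the provider for active-arm rows, a code, and an empty participant-ID cell. Provider names are removed from the public copy.

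Two other passages bear on concealment and blinding:

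- Table 1.0 (section III.C) describes the initial assignment as "Assigned by sealed envelope opened by participant after site visit". Its wait-list row mentions randomisation after 7 weeks but no envelope.
- Section V.A promises: "The assessors will remain blind to treatment condition throughout the study". No mechanism is given.

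The documents do not say who holds Appendix C, or that it is kept from recruiters, therapists or assessors.

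**The concern.** Concealment requires that nobody who decides whether, or when, a person enters can know the next assignment. A sealed envelope does this only if the list behind it is out of reach. Here the list is an appendix to the document that governs the trial.

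Foreknowledge could matter in three places:

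- **Entry.** Some judgement and timing precede allocation. Subthreshold PTSD is admitted (section III.A), and a recent change in psychotropic medication leads to a wait of at least 30 days (section IV.B). Knowing the next arm could affect who enters, or when.
- **End of the wait.** This CAPS is the WL outcome and also the pre-treatment value for the second stage (section V.B). The week-7 call script in Appendix A makes the later assignment conditional on the participant still qualifying. Rating and eligibility check both come after the next therapy is already readable.
- **Assessment.** Post-doctoral fellows conduct all assessment interviews (section V.A), and section VIII.A allows a coordinator, a post-doctoral fellow or both to screen. The same staff group may therefore do both. If the empty ID column is filled in, the table links participant to arm directly.

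At stake are selection bias in the randomised comparisons and bias in CAPS ratings, the primary outcome.

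**Working it through.** **1. Reproduce the plan's own total.** Section III.E.2 gives N = 240, split equally between the two active treatments. Counting rows in Appendix C:

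| Table | Rows | WL | CPT | ART |
|---|---|---|---|---|
| UC, first stage | 48 | 16 | 16 | 16 |
| VA, first stage | 192 | 64 | 64 | 64 |
| UC, after WL | 16 | – | 8 | 8 |
| VA, after WL | 64 | – | 32 | 32 |

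First stage: 48 + 192 = 240. Second stage: 16 + 64 = 80. Final CPT: 16 + 64 + 8 + 32 = 120; final ART is the same. The printed list is therefore the complete allocation for the N = 240 design. Sections III and IV.A plan 280 participants, so 280 − 240 = 40 have no printed assignment.

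**2. Check the link between stages.** All 80 WL codes (16 UC, 64 VA) reappear in the second-stage tables in the same order with -2 added. At UC, for example, VJ8 is WL and VJ8-2 is CPT; RG0 is WL and RG0-2 is ART. Site and first-stage code are enough to read the later therapy. Three codes (GA9, GF7, NN5) occur at both sites with different arms, so the site must be known for those.

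**3. Compare predictability.** With the list and the site's running count, and rows used in printed order, every next assignment is known. As a yardstick, the same block sizes were simulated with the list hidden. The guesser knows the block size and all earlier assignments and always picks the arm with most places left, with ties split evenly (4,000 simulated lists per block size).

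| Block | Arms | Chance | Best guess, list hidden | List and count known |
|---|---|---|---|---|
| VA, 192 | 3 | 0.333 | 0.386 | 1 |
| UC, 48 | 3 | 0.333 | 0.435 | 1 |
| VA, 64 | 2 | 0.500 | 0.571 | 1 |
| UC, 16 | 2 | 0.500 | 0.627 | 1 |

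The block sizes themselves are not the problem, since a hidden list with these blocks would be only modestly guessable. The printing of the list is what matters.

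**4. Who could know the count.** All phone screens for both sites are run from the VA (section IV.E.1), so one staff group sees the inflow to both.

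**The case against.** The strongest reply is that a list's place in a document does not show who received it. Site staff may have worked from a copy without the appendix, and a list made public after enrolment harms nobody. This stands as far as it goes: the documents show neither distribution nor withholding.

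A reader might infer that concealment and assessor blinding have failed, or that any holder of the protocol can read the next assignment. The documents support neither:

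- Because the ID cells are empty, a reader needs the site's running count or a participant's code as well.
- Strict top-to-bottom use of the rows is an inference. Active rows also carry a therapist, and nothing says what happens if that therapist is unavailable.
- The appendix says only code; nothing ties the codes to the envelopes or to assessors' paperwork.
- No passage says that enrolling or assessing staff work from a copy containing Appendix C.

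Fixing the post-wait therapy in advance is also harmless in itself. It amounts to randomising to WL-then-CPT or WL-then-ART (8 + 32 = 40 each). Only foreknowledge can bias it.

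The planned adjustment for baseline PTSD would remove bias that acts through measured baseline severity. It would not remove bias through unmeasured prognosis, or through a baseline rating made with the next arm known.

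What remains is more than missing detail. The plan places the ordered list in the protocol, directs second-stage allocation from it, and describes no concealment step there.

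**Conclusion.** The point holds as a weakness in safeguards. Concealment is not assured at the first stage, where the envelope protects only against people without the list. It is weakest at the second, where no envelope is described and the WL code discloses the next therapy during the wait. Assessor blinding is at risk, but no breach is shown.

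The exposure is 240 first-stage and 80 second-stage assignments. Each is fully predictable to someone with the appendix and the running count (or, for second-stage assignments, the site and WL code), assuming that rows are used in order. The documents give no basis for sizing any resulting bias in CAPS, so none is offered. The trial should make this change; the point does not show that its results are biased.

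**What to change.** 1. Remove Appendix C from the protocol and state only the method: 1:1:1 by site, then 1:1 after WL, with random therapist allocation as in section VII.A.
2. Have the existing statistician, or another person with no role in recruitment, therapy or assessment, hold the list and release assignments one at a time at both stages.
3. Conceal the second-stage assignment until the end-of-wait assessment and eligibility check are complete, and use codes that cannot be read across from the WL code.
4. State that enrolling staff and assessors have no access to the list.
5. Regenerate all rows not yet used, including provider allocation, with codes unique across sites. Prepare any rows for the oversample of up to 40 in the same way.

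The cost is one amendment and a new list from the existing statistician, with no extra staff or visits. The documents do not give enrolment status. New rows protect only assignments not yet made; for the rest, the trial report should state who had access to the list and when.
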